## **8. RESEARCH QUESTION AND OBJECTIVES**

The aim of this study is to describe the baseline demographic and clinical characteristics, and HRU of adult ( $\geq 18$  years) COVID-19 patients who have been prescribed nirmatrelvir, ritonavir treatment in the outpatient setting.

Primary objective:

1. To describe the baseline demographic and clinical characteristics, including pre-existing comorbidities, of adult COVID-19 patients treated with and those not treated with nirmatrelvir, ritonavir.

Secondary objectives:

1. To evaluate the number and proportion of COVID-19 patients who meet the most up-to-date WHO recommendations for the use of therapeutics in the treatment of COVID-19 (ie, version 14, published 10Nov2023) in comparison to Kingdom of Bahrain national recommendations.
2. To assess adult COVID-19 patients' HRU and outcomes within the 28-day period

Exploratory objective:

1. To assess HRU and outcomes at day 5, 7 and 21 as exploratory analyses

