## 1.2 STUDY OBJECTIVES

The overall aim of this study is to examine the baseline demographic, clinical, and outcome characteristics of COVID-19 patients who received Paxlovid.

PFIZER CONFIDENTIAL

CT24-WI-GL03-RF03 2.0 *Non-Interventional Statistical Analysis Plan For Secondary Data Collection*  
*Study 01-Jun-2020*  
Page 6 of 22

The objectives are

- (i) to describe the demographic, clinical, and outcome characteristics of COVID-19 patients who received Paxlovid and COVID-19 patients who were offered, but refused Paxlovid
- (ii) to examine differences in the demographic characteristics (e.g., age, sex, nationality, type of outpatient encounter, vaccination status) between COVID-19 patients who received Paxlovid and COVID-19 patients who refused Paxlovid,
- (iii) to examine differences in the clinical characteristics (e.g., comorbidities, symptoms, duration of symptoms) between COVID-19 patients who received Paxlovid and COVID-19 patients who refused Paxlovid over a five-day follow-up,
- (iv) to examine differences in outcomes (e.g., hospitalisations, time spent in an intensive care unit, time spent with invasive mechanical ventilation, supplemental oxygen usage, re-admission to hospital, deaths) between COVID-19 patients who received Paxlovid and COVID-19 patients who refused Paxlovid over a five-day follow-up.
- (v) To examine differences in the proportion of COVID-19 patients who meet the most up-to-date WHO recommendations for the use of therapeutics in the treatment of COVID-19 (ie, version 14, published 10Nov2023) in comparison to Kingdom of Bahrain national recommendations.

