## **STATISTICAL METHODOLOGY AND STATISTICAL ANALYSES**

### **1.12 STATISTICAL METHODS**

Descriptive statistics will be presented separately for the demographic, clinical, and outcome characteristics of COVID-19 patients taking Paxlovid, and for COVID-19 patients who were offered Paxlovid therapy but who refused treatment. Inferential statistics will be used to assess any differences in demographic characteristics, clinical characteristics, and disease outcomes between patients who received Paxlovid and patients who refused Paxlovid.

PFIZER CONFIDENTIAL

CT24-WI-GL03-RF03 2.0 *Non-Interventional Statistical Analysis Plan For Secondary Data Collection*  
*Study 01-Jun-2020*  
Page 13 of 22

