### Inferential statistics

Between-group differences in categorical variables will be examined using proportions tests, Chi-square tests of independence or Fisher exact tests as appropriate. Differences in continuous variables will be examined using independent t-tests.

Differences in proportions or means (as appropriate) and 95% confidence intervals between COVID-19 patients taking Paxlovid, and COVID-19 patients who were offered Paxlovid therapy but who refused treatment will be reported. Additionally, Cramer's V or Cohen's d will be reported.

Cramer's V is a measure of association that quantifies the strength and direction of the relationship between the two categorical variables being compared. Cramer's V ranges from 0 to 1, where 0 indicates no association between the variables, and 1 represents a perfect association. The magnitude of Cramer's V will be interpreted as follows:

Cramer's V	Effect Size
-------------------	--------------------

0.1	Weak
0.3	Medium
0.6	Large

Cohen's d quantifies the standardized difference between the means of the two groups, and is calculated by taking the difference between the means of the two groups and dividing it by the pooled standard deviation. The magnitude of Cohen's d will be interpreted as follows:

Cohen's d	Effect Size
------------------	--------------------

0.2	Small
0.5	Medium
0.8	Large

An a priori alpha level of 0.05 has been selected for all tests. As this work is exploratory no adjustment for multiple comparisons will be made.

PFIZER CONFIDENTIAL

CT24-WI-GL03-RF03 2.0 *Non-Interventional Statistical Analysis Plan For Secondary Data Collection*  
Study 01-Jun-2020  
Page 14 of 22

Selection of the control groups will consider the following characteristics based on the availability of data using propensity-score matched:

- age,
- sex,
- COVID vaccination status,
- high-risk status for severe COVID-19 outcomes (WHO definition),
- assessment of healthcare seeking behavior in 365 days prior to COVID infection (such as flu or streptococcus pneumoniae vaccine, has primary healthcare provider, number of primary care/hospital visits),
- socioeconomic factors (such as household income, employment status),
- geographic location of residence,
- comorbidities.

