### **7.2.3 Summary of Analyses**

Descriptive statistics will be presented for all variables. Inferential statistics will be used to examine difference in demographic, clinical, and outcome characteristics between COVID-19 patients who received Paxlovid and those who were offered, but refused, Paxlovid.

PFIZER CONFIDENTIAL

CT24-WI-GL03-RF03 2.0 *Non-Interventional Statistical Analysis Plan For Secondary Data Collection*  
*Study 01-Jun-2020*  
Page 15 of 22

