**LIST OF TABLES AND TABLE SHELLS****Table 3: Descriptive statistics for baseline variables**

Variables	Group		P-value	Effect size
	Paxlovid	Control		
Age, % (n)				
18-29				
30-49				
50-64				
65-74				
≥75 years				
Gender, % (n)				
Male				
Female				
Nationality, % (n)				
Bahrain				
Other Middle East and North Africa				
India				
Pakistan				
South East Asia				
Caucasian				

PFIZER CONFIDENTIAL

CT24-WI-GL03-RF03 2.0 *Non-Interventional Statistical Analysis Plan For Secondary Data Collection Study* 01-Jun-2020  
 Page 16 of 22

Enrollment Date Place of Service (POS), % (n)				
Office visit				
Emergency room				
Outpatient hospital				
Other				
Specialty of Provider at enrollment Date				
Interns				
Residents				
Family Phyiscans				
Specialist				
Consultants				
Number of days from COVID-19 symptom onset to resolution, mean (SD)				
Number of days from vaccination to contracting COVID-19, mean (SD)				
Number of days from contracting COVID-19 to being prescribed Paxlovid, mean (SD)				
Number of days from COVID-19 test to Paxlovid treatment, mean (SD)				
COVID-19 Lab Tests with Positive Result, % (n)				
COVID-19 Lab Test with Variant Type, % (n)				

PFIZER CONFIDENTIAL

CT24-WI-GL03-RF03 2.0 *Non-Interventional Statistical Analysis Plan For Secondary Data Collection Study* 01-Jun-2020  
 Page 17 of 22

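### The SAP's propensity-score selection of controls uses characteristics that the study sets out to compare, and no table is assigned to matched or unmatched groups

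*SAP*

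**What the plan says.** The protocol's primary objective (section 8) is "To describe the baseline demographic and clinical characteristics, including pre-existing comorbidities, of adult COVID-19 patients treated with and those not treated with" the study drug. SAP section 1.2 turns this into comparisons. Objective (ii) is "to examine differences in the demographic characteristics (e.g., age, sex, nationality, type of outpatient encounter, vaccination status" and so on, between recipients and refusers. Objective (iii) does the same for clinical characteristics, with comorbidities and symptoms as examples.

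SAP section 1.12 first says "Descriptive statistics will be presented separately for the demographic, clinical, and outcome characteristics of COVID-19 patients taking Paxlovid" and, separately, for those who refused it. It then adds: "Inferential statistics will be used to assess any differences in demographic characteristics, clinical characteristics, and disease outcomes between patients who received Paxlovid" and those who refused. Section 7.2.3 repeats that scope.

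At the end of Inferential statistics, after the tests and effect sizes, comes: "Selection of the control groups will consider the following characteristics based on the availability of data using propensity-score matched". The eight bullets that follow are age, sex, COVID vaccination status, WHO high-risk status, healthcare-seeking behaviour in the previous 365 days, socioeconomic factors, place of residence, and comorbidities. No ratio, caliper, replacement rule or balance criterion is given.

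The full analysis set (section 1.5) is about 8263 patients, including about 3000 treated and about 1000 refusers. Other analysis sets (1.7) and covariates (1.11) are marked not applicable. The shells for "Table 3: Descriptive statistics for baseline variables" and for Table 6 (clinical characteristics) each have one Paxlovid column, one Control column, a P-value and an effect size. Neither is labelled matched or unmatched.

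**The concern.** Matching on a variable is meant to remove the group difference in that variable. Here, differences in several of the matching variables are themselves results that the study promises to report. A P-value and effect size for age or comorbidity taken from groups matched on age and comorbidity say little about who accepts and who refuses treatment.

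The opposite reading has its own cost. If the matching sentence has no effect, nothing else in the SAP adjusts the outcome comparison for differences in risk between recipients and refusers. Two analysts could both follow the SAP and produce different baseline tables and different outcome tables.

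**Working it through.** The plan contains no sample-size or power figure to reproduce on this point. The check has four steps.

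**1. Overlap between matching factors and compared characteristics.**

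| Factor listed for matching | Where it is compared | Variable in SAP Tables 1, 2 or 4 |
|---|---|---|
| Age | Objective (ii); Table 3 | Yes |
| Sex | Objective (ii); Table 3 | Yes |
| Vaccination status | Objective (ii); Table 6 | Yes (dates) |
| Comorbidities | Protocol primary objective; objective (iii); Table 6 | Yes |
| WHO high-risk status | Paxlovid and Control rows of Table 8; related risk factors in Table 6 | Yes (risk factors) |
| Healthcare-seeking behaviour | No row | None as the bullet describes it |
| Socioeconomic factors | No row | None |
| Residence | No row | None |

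Four of the eight are named as compared in objectives (ii)-(iii), and the table shells add a fifth. The bullet "socioeconomic factors (such as household income, employment status" and the one on residence have no variable to extract.

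**2. If the matching sentence is applied to control selection.** The group sizes of 3000 and 1000 come from the SAP. The baseline gaps are assumed, because the documents give none: age 55 against 51 years (SD 14, so 4/14 = 0.29 SD), one sex 50% against 55%, vaccinated 92% against 85%, comorbidity 55% against 45%.

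Method: 200 simulated data sets; logistic propensity score; 1:1 nearest neighbour on the logit without replacement; caliper 0.2 SD of the logit; refusers in random order each take the nearest unused treated patient; each pair is counted once.

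- Unmatched: standardised differences 0.28, -0.10, 0.22 and 0.20; p < 0.05 in 100%, 78%, 100% and 100% of runs.
- Matched (mean 993 pairs): mean absolute standardised differences 0.016 to 0.020; p < 0.05 in 0% of runs for all four.

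The size depends on settings that the SAP leaves open:

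- For assumed age gaps of 0.2, 0.3 and 0.5 SD, 1:1 matching without a caliper leaves about 0.00 to 0.04 SD when refusers choose treated patients. When treated patients in random order choose refusers it leaves 0.23, 0.33 and 0.45 SD, which is essentially no change.
- Three treated per refuser without a caliper uses everyone (3 × 1000 = 3000), so the gap is unchanged.
- Three per refuser with a 0.2 SD caliper leaves 0.09, 0.13 and 0.20 SD if controls are unweighted, and about zero if each control is counted once per matched pair.

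**3. If it is not applied.** The tests are proportion tests, chi-square, Fisher and independent t-tests, with no covariates. Protocol section 9.7 quotes WHO hospitalisation rates of 6% (high risk), 3% (moderate) and 0.5% (low). With these taken as true in both groups and no treatment effect, the spurious difference is the difference in share multiplied by the difference in rate:

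- 10 points more at high rather than moderate risk: 0.10 × (6 - 3) = 0.30 percentage points
- 10 points more at moderate rather than low risk: 0.10 × (3 - 0.5) = 0.25
- 20-point differences: 0.20 × 3 = 0.60 and 0.20 × 2.5 = 0.50

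For scale, a group wholly at moderate risk would show 3.00%, and one with 10% at high risk 0.9 × 3 + 0.1 × 6 = 3.30%.

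**4. The pool to match from.** Protocol section 9.1 and Table 1 define controls as any untreated patient. SAP section 1.1 and its Study population text define them as patients offered Paxlovid who refused. The SAP calls about 3000 treated about 53% of those eligible, while the protocol (9.5) gives 8263 eligible with at least 3000 treated:

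- 3000/8263 = 36.3%
- 0.53 × 8263 = 4379
- 3000/0.53 = 5660
- In neither SAP group: 8263 - 3000 - 1000 = 4263 (51.6%), or 8263 - 4379 - 1000 = 2884 (34.9%)

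**The case against.** The best defence is that the tables are meant to be unmatched. The SAP defines one analysis set and no other, its descriptions of the refusers do not mention matching, and the matching sentence stands apart from the Descriptive statistics heading. The sentence is also hedged: selection will consider the factors, subject to data availability. The study has no hypotheses or decision rules, calls itself exploratory, and the protocol limits its claims to association. The protocol's silence on matching is no fault, since section 9.7 leaves detailed methods to the SAP.

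Much of this stands. A reader might infer that the SAP commits its baseline tables to matched groups; it does not, and the unmatched reading is open. The heading does not settle the matter, though: sections 1.12 and 7.2.3 apply inferential statistics to demographic and clinical characteristics too, and those P-values share rows with the descriptive figures. The sentence also speaks of selecting controls, not of adjusting an outcome test.

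Three other stronger readings fail:

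- That matching would always remove the differences. Step 2 shows settings that leave them intact.
- That about 2000 treated patients would be dropped. The SAP says about 3000 will be included, and about 1000 may be the resulting control group rather than the pool to match from.
- That all five overlapping factors are named in objectives (ii)-(iii). Only four are; WHO high-risk status rests on the shells, and objective (v) is worded as WHO against national recommendations.

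**Conclusion.** The concern holds as a conflict in the SAP that should be fixed before analysis. It does not make the study invalid. Applied as written, the selection rule reduces the differences that objectives (ii)-(iii) report, to near zero with a 0.2 SD caliper under the assumed gaps and by an amount ranging from nothing to nearly all of the gap under other settings. Not applied, it leaves the outcome comparison open to case-mix differences of about 0.25 to 0.60 percentage points in hospitalisation for 10- to 20-point differences in risk mix. Those figures assume the quoted WHO rates and no treatment effect; the actual risk mix of the two groups is not in the documents, so neither the size nor the direction of the bias is known. The mismatch between 53% and 36.3% and the two control definitions follow directly from the documents, which do not show which figure or definition is wrong.

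**What to change.** 1. State that the baseline rows of Tables 3 and 6, including symptoms at presentation, and Table 8 use all treated patients and all controls, unmatched.
2. Confine propensity-score matching or weighting to outcomes: Table 7, the death rows of Table 6, the symptom-resolution row of Table 3, and any follow-up symptom rows. Show follow-up symptoms separately from symptoms at presentation; Table 6 does not separate them, although objective (iii) refers to a five-day follow-up. Use only extracted pre-treatment covariates and list them under Covariates. State the ratio, caliper, matching order and replacement rule, or the type of weight. Report standardised differences before and after, and use an analysis that reflects the matching or weights.
3. Reconcile about (or at least) 3000, 53% and 8263, account in a flow table for patients in neither group, and align the protocol's control definition with the SAP's.

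The cost is SAP wording and a modest amount of extra analysis, with no new patients. The downside is that matching may drop some patients from the outcome comparison, and weighting may need extreme weights trimmed.

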**Table 1. Cohort Definitions**

Name	Criteria	Identification Period	Index Date	Follow Up Period
Treated patients	Patients diagnosed with COVID-19 and treated with Paxlovid™	After Paxlovid™ availability during the same dominant variant (ie, Omicron or Delta etc.) era timeframe as Cohort	Paxlovid™ prescription written date or dispense date*  If neither of the above are available, the COVID-19 diagnosis date may be used as the index date	28 -days follow up
Control group	Patients diagnosed with COVID-19 and not treated with Paxlovid™	After Paxlovid™ availability during the same dominant variant (ie, Omicron or Delta etc.) era timeframe as Cohort	Date of COVID-19 diagnosis	28 -days follow up

\*If both dates are available in the data source, the most recent date should be used as the index date for Cohort.

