### 9.2.2. Exclusion Criteria

**There are no exclusion criteria for this study.**

## 9.3 Variables

The following variables are used to obtain comprehensive descriptive results.

1. Demographics
2. Date of symptoms
3. Viral variant analysis where available (type of viral variant ie, omicron, delta etc.)
4. PCR date along with CT Value

5. Co-morbidities and
6. BMI if  $\geq 30$
7. Symptoms at presentation
8. COVID 19 vaccine status (NB 92% of population has been vaccinated -with at least one dose of COVID 19 vaccine- in Bahrain)
9. Hospital admission
10. Follow up looking at compliance and reason of non-compliance
11. Day 5,7, 21 and 28 symptoms for COVID-19 patients who receive and HRU limited to admission (ICU, ward, need for oxygen therapy) or death
12. Date of symptoms resolution if applicable

**Table 2** Table 2 below depicts the patient demographics that will be accessed during the baseline and follow-up periods. The baseline period is defined as one year before the index date. Comorbidities (full list in [Table 6](#)) and maintenance medication usage for chronic conditions (eg, statins, antihypertensives, etc.) will be described during the baseline period and follow-up periods and are listed in [Table 3](#).

Risk factors for severe COVID-19, intensive care unit (ICU) usage, invasive mechanical ventilation (IMV) usage, supplemental oxygen use, non-invasive ventilation, and high-flow nasal cannula usage are depicted in [Table 5](#) and will be extracted from the *I-Seha* national electronic health record database.

Where applicable, emerging treatment patterns may be assessed as the time from symptom onset to COVID-19 diagnosis, time from symptom onset to treatment initiation, and the time from COVID-19 diagnosis to treatment initiation as illustrated in [Table 5](#).

10Nov23 WHO recommendations for Paxlovid treatments to define: 1. COVID-19 patients who meet the WHO criteria for “strongly recommended” 2. COVID-19 patients who meet the WHO criteria for “conditionally recommended”, and 3. COVID patients who are not falling into categories 1 or 2 will be used.

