**Table 2. Patient Demographic and Clinical Characteristic Variables at Index**

Variable	Operational definition
Age	Age will be defined as of the index date and will be used to assign patients to age groups: 18-29, 30-49, 50-64, 65-74, $\geq 75$ years and unknown/missing age.
Gender	Defined as of the index date as the distribution of female, male and unknown/missing sex patients.
Region	Kingdom of Bahrain
Nationality	Nationality of the patient will be mentioned
Enrollment Date Place of Service (POS)	Distribution of patients by the type of outpatient encounter during the enrollment date (eg, office visit, emergency room (ER), outpatient hospital, other, etc.).
Enrollment Date	Date (defined as MM/YYYY) of the enrollment date specified for each Cohort.

Variable	Operational definition
Specialty of Provider at enrollment Date	Distribution of the provider specialties present during the enrollment date. Patients with no provider specialty recorded will be included in an “Unknown/missing specialty” category.
Patient-reported COVID-19 symptoms	
List of COVID-19 symptoms to be added by study team (US, CDC definition).
 
1- Stuffy or runny nose 2- Sore throat 3- Shortness of breath 4- Cough 5- Low energy/tiredness/fatigue 6- Muscle ache/body aches 7- Headache 8- Chills or shivering 9- Feeling hot/feverish 10- Nausea or vomiting 11- Diarrhea 12- Loss of sense of smell 13- Loss of sense of taste

COVID-19 Symptom Onset Date	Date of symptom onset during the post-Paxlovid™ availability timeframe.
Time to COVID-19 Symptom Resolution	The number of continuous days with the same COVID-19 symptom. When available, the number of consecutive days will be reported as counts and percentages. The date of symptom resolution (last date recorded) will be reported when available.
Date of COVID-19 Vaccination	Date of each COVID-19 vaccination received. Note: patient-specific vaccination history may require more than 6-months pre-index time period.
Date of Paxlovid™ prescription written and/or fill history (eg, prescription claim)	Date of Paxlovid™ prescription written or fill history. Note: if both dates are available within the database, use the most recent date provided.

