## 9.5. Study Size

This is a retrospective observational study using a sample afforded by the I-Seha Electronic health record. While this study will be descriptive in nature, feasibility queries show that, between 16 February 2022 and 30 November 2022, there were 8263 patients that met all study inclusion and exclusion criteria eligible for Paxlovid™ therapy of whom at least 3000 patients were treated with Paxlovid™ therapy and 1000 were not. All records from the participant cohort of 8263 will be reviewed.

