### **Study population**

Patients will be eligible for inclusion in the study if they were diagnosed with COVID-19 between February and November 2022, were treated in an outpatient setting in the Kingdom of Bahrain, and were offered Paxlovid. Paxlovid was offered to patients in the Kingdom of Bahrain if they were at high risk of complications from COVID-19 due to age  $\geq$  50 years, BMI  $\geq$  35, or a medical history of chronic kidney disease (eGFR  $\geq$ 30 ml/min), diabetes mellitus, primary or secondary immunosuppressive disease or receiving immunosuppressive treatment, cardiovascular disease or hypertension, chronic lung diseases, sickle cell disease, neurodevelopmental disorders, or having a medical-related technological dependence. There are no exclusion criteria.

EHRs from approximately 3000 COVID-19 patients who were treated with Paxlovid, all of whom gave verbal consent for treatment that was recorded in the medical record, will be included in the study. These patients were treated between February and November 2022, and consist of approximately 53% of the total eligible patient population from the timeframe. A comparison group of patients will also be included. This group will consist of approximately 1000 patients with COVID-19 that were offered Paxlovid therapy but who refused treatment, over this same time period.

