**Table 1: Patient Demographic Variables**

Variable	Operational definition
Group	Received Paxlovid or did not receive Paxlovid
Age	Age will be defined as of the date of COVID-19 diagnosis using a PCR test and will be used to assign patients to age groups: 18-29, 30-49, 50-64, 65-74, $\geq 75$ years and unknown/missing age
Sex	Female, male and unknown/missing sex patients
Nationality	Nationality of the patient (Bahrain, other Middle East and North Africa, India, Pakistan, South East Asia, Caucasian)
Enrollment Date Place of Service (POS)	Type of outpatient encounter during the enrollment date (e.g., office visit, emergency room (ER), outpatient hospital, other, etc.)
Enrollment Date	Date (defined as MM/YYYY) of the enrollment date specified
Specialty of Provider at enrollment Date	Provider specialties present during the enrollment date. Patients with no provider specialty recorded will be included in an “Unknown/missing specialty” category
COVID-19 Symptom Onset Date	Date of symptom onset prior to presentation to healthcare facility

PFIZER CONFIDENTIAL

CT24-WI-GL03-RF03 2.0 *Non-Interventional Statistical Analysis Plan For Secondary Data Collection*  
*Study 01-Jun-2020*  
 Page 8 of 22

Time to COVID-19 Symptom Resolution	Time from onset of COVID-19 symptoms to resolution of symptoms
Date of COVID-19 Vaccination	Date of each COVID-19 vaccination received. Note: patient-specific vaccination history may require more than 6-months pre-index time period.
Date of Paxlovid prescription written and/or fill history (e.g., prescription claim)	Date of Paxlovid prescription written or fill history. Note: if both dates are available within the database, use the most recent date provided.

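### The SAP's propensity-score list omits calendar month of diagnosis, so treated patients and refusers may be distributed differently across the 9.5-month window

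*SAP*

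**What the plan says.** SAP section 1.13, under Inferential statistics, states: "Selection of the control groups will consider the following characteristics based on the availability of data using propensity-score matched". Eight items follow: age, sex, vaccination status, WHO high-risk status, healthcare-seeking behaviour, socioeconomic factors, place of residence and comorbidities. SAP sections 1.8 (Subgroups) and 1.11 (Covariates) are both marked not applicable.

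On calendar time, the identification period in Protocol Table 1 reads, for both cohorts, "After Paxlovid™ availability during the same dominant variant (ie, Omicron or Delta etc.) era timeframe as Cohort". No era dates are attached. Protocol section 9.5 reports that "between 16 February 2022 and 30 November 2022, there were 8263 patients that met all study inclusion and exclusion criteria". The SAP's Study population section gives the window as February to November 2022 and takes as controls patients "offered Paxlovid therapy but who refused treatment, over this same time period".

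The dates needed are already planned:

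- Protocol Table 2: "Date (defined as MM/YYYY) of the enrollment date specified for each Cohort". SAP Table 1 repeats this.
- Protocol section 9.3: "PCR date along with CT Value".
- SAP Table 1, for symptom onset: "Date of symptom onset prior to presentation to healthcare facility".

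The SAP's Endpoints and Covariates section makes all extraction conditional on availability.

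**The concern.** The protocol makes variant era part of how both cohorts are identified, so it accepts that epidemic timing bears on comparability. The SAP carries this forward only as a common outer window. Nothing in the matching aligns treated patients and refusers inside it.

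Two things can move over 9.5 months: the willingness of eligible patients to accept a newly authorised drug, and the background risk of admission. If both moved, month of diagnosis would be associated with group and with outcome, and would confound the comparison. None of the eight listed characteristics stands in for it.

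This matters because the comparison is more than descriptive. Protocol section 9.1 says resource use will be compared between the groups. The SAP plans tests, p-values, effect sizes and 95% confidence intervals on hospitalization and the other outcomes.

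**Working it through.** **1. Is calendar time controlled anywhere in the SAP?** It is not among the eight items, there are no covariates and there are no subgroups. The only restriction is the shared window.

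**2. Length of the window.** 16 February to 30 November 2022 inclusive: 13 + 31 + 30 + 31 + 30 + 31 + 31 + 30 + 31 + 30 = 288 days. 288 / 30.4375 = 9.46 months.

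**3. How large could the effect be?** The documents contain no figure to reproduce: no monthly risk, no monthly uptake and no power calculation. What follows is an illustration with no drug effect.

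Split the window into an early and a late half. Let r be the early-to-late ratio of admission risk, and let pT and pC be the shares of treated patients and refusers diagnosed early. The spurious risk ratio is

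RR = (pT·r + 1 − pT) / (pC·r + 1 − pC)

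| pT | pC | RR at r = 2 | RR at r = 3 |
|---|---|---|---|
| 0.3 | 0.6 | 1.3/1.6 = 0.81 | 1.6/2.2 = 0.73 |
| 0.4 | 0.5 | 1.4/1.5 = 0.93 | 1.8/2.0 = 0.90 |
| 0.5 | 0.4 | 1.5/1.4 = 1.07 | 2.0/1.8 = 1.11 |
| 0.6 | 0.3 | 1.6/1.3 = 1.23 | 2.2/1.6 = 1.38 |

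Whenever pT = pC, RR = 1.00 for any r. That is what balancing on month would achieve in this model.

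**4. Would it register as a significant result?** Take 1000 refusers, 3000 treated patients and two-sided alpha 0.05 (the SAP does not state sidedness). The early and late risks are assumed. The 3% and 0.5% values borrow the size of the WHO moderate- and low-risk hospitalization rates quoted in the SAP, which are not calendar-period rates.

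| Early / late risk | Early share, treated vs refusers | Group risks | RR | Chance of p < 0.05 in that direction |
|---|---|---|---|---|
| 3% / 2% | 45% vs 55% | 2.45% vs 2.55% | 0.96 | about 4% |
| 3% / 1.5% | 40% vs 60% | 2.10% vs 2.40% | 0.875 | about 9% |
| 3% / 1.5% | 30% vs 70% | 1.95% vs 2.55% | 0.765 | about 22% |
| 3% / 0.5% | 30% vs 70% | 1.25% vs 2.25% | 0.56 | about 60% |

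With no imbalance, the chance in one direction is half of alpha, 2.5%. Mild imbalance therefore does little. The last row needs a sixfold risk gap as well as a strongly uneven split.

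**5. What do the table shells show?** SAP Table 3 has no row for month of diagnosis and none for onset to diagnosis. Its symptom row runs from onset to resolution, which is an outcome. Two timing rows end at Paxlovid prescription or treatment and are undefined for refusers. There is a variant-type row, but variant is recorded only when available and does not give the month within an era.

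**The case against.** The strongest reply has four parts.

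*The era condition still stands.* A reader might infer that the SAP breaks the protocol's same-variant requirement. The documents do not support that. The SAP does not withdraw the condition, both groups share one window, and nothing shows more than one dominant variant within it. What remains is possible imbalance inside the window.

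*The imbalance would not be hidden.* A reader of the Table 3 shell might conclude that it could never be seen. That goes too far. SAP section 1.12 presents descriptive statistics separately by group, and section 7.2.3 promises them for all variables. Enrollment month and onset date are both listed variables. The gap is a missing shell row and a missing matching variable. However, seeing an imbalance after matching does not remove it.

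*The study is exploratory.* There are no hypotheses, Protocol section 9.9 limits conclusions to association, and the SAP calls the work exploratory. This lowers the stakes. It does not remove the point, because the SAP chose propensity-score matching to make the groups comparable and then tests outcomes between them.

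*Illness stage is weaker ground.* It is tempting to add that late presenters decline treatment more often and that this distorts the result. The documents say nothing about who declines, and the figures above cover calendar time only. Matching on days from onset to diagnosis would also not align illness day at the start of follow-up. Protocol Table 1 indexes treated patients at prescription or dispensing (diagnosis only if neither date exists) and controls at diagnosis. Onset dates may be incomplete for refusers: Protocol section 9.4.1 describes the symptom call after treatment initiation, and for untreated patients lists re-evaluation, admission or death. The SAP does not impute. Requiring an onset date could therefore remove refusers selectively. This part of the objection stands, and onset timing belongs in a secondary role.

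**Conclusion.** The point holds for calendar month. It is absent from the SAP's only confounding control, the dates are already to be collected, and the protocol itself treats epidemic era as relevant. A shared 9.5-month window leaves the within-window distribution free to differ between treated patients and refusers.

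The size and direction of any bias cannot be determined. The range of about 0.73 to 1.38 rests wholly on assumed early shares of 30% to 60% and a two- to threefold change in risk. The milder splits give 0.90 to 0.93, or 1.07 to 1.11 when reversed. A reader might infer a bias in favour of Paxlovid; the documents give no basis for choosing a direction. The change should be made because it is cheap and specific, not because a large error has been shown.

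**What to change.** **Main change.** In SAP section 1.13, add calendar month of COVID-19 diagnosis to the matching characteristics, matched exactly or within one month. Derive it from the PCR date, with enrollment month as a fallback. Add a between-group row for month of diagnosis to SAP Table 3.

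**Secondary.** Report days from symptom onset to diagnosis, and from symptom onset to the index date, by group and with the number missing. Let onset timing enter the propensity score only where recorded, for example with a missing category or as a sensitivity analysis, so that refusers without an onset date are kept.

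**Cost.** The main change needs one matching variable and one table row from data already planned. Some patients may have no close-month match and leave the matched set; their number should be reported. Completeness of onset dates among the roughly 1000 refusers is unknown, so the loss from requiring one cannot be assumed small.
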